### **9.8.5 Contraception**

In the reproduction phase of toxicology studies conducted in juvenile rats, there were no adverse ELX-02-related effects noted on sexual maturation, reproductive and fertility indices, maternal uterine examinations, or sperm evaluations. However, since there are no adequate and well-controlled studies with pregnant women, it is uncertain whether there is human fetal risk associated with the use of ELX-02. However, aminoglycosides are known to be associated with fetal deformities, therefore, non-pregnant, non-lactating females will be included in the study. Female subject of childbearing potential will be included only if they use appropriate methods of contraception.

Male subjects who are not vasectomized will also be required to use appropriate methods of contraception during the study to avoid pregnancies in their female partners. Male subjects (including men who have had vasectomy) with a pregnant partner must agree to use a condom to prevent *in utero* drug exposure.

## **9.9 Sample Collection for Pharmacokinetic Evaluation**

### **9.9.1 Blood Sample Collection and Processing**

A total of 13 blood samples will be drawn from each subject of Groups 1 to 4 for PK analyses. Blood samples will be collected 0.25, 0.5, 0.75, 1, 2, 4, 6, 12, 24, 36, 48, 72, and 168 (Day 8) hours post-dose (up to 6 mL for each sampling time).

The time tolerance window for blood samples will be  $\pm 1$  minute for timepoints up to 2 hours post-dose;  $\pm 5$  minutes from 4 hours to 12 hours;  $\pm 10$  minutes from 24 hours to 72 hours; and  $\pm 24$  hours for the 168-hour sample. Sample collections done outside the pre-defined time windows will not be considered as protocol deviations since actual post-dose sampling times will be used for PK and statistical analyses. Unless otherwise specified or for subject safety, when blood draws and other procedures coincide, blood draws will have precedence. A saline intravenous catheter may be used for blood collection to avoid multiple skin punctures, when appropriate. Otherwise, blood samples will be collected by direct venipuncture.

The total volume of blood including that collected for eligibility and safety purposes should not exceed 196 mL for the whole study (refer to [Table 3](#) for details). Deviations related to the volume of blood collected will be reported only when the total volume collected from a subject for the whole study is exceeded.

**Table 3. Blood Volume for Laboratory Analyses**

Analysis	Approximate Amount of Blood per Sample (mL)	Number of Timepoints	Total Amount of Blood (mL)
Hematology	4	3	12
Biochemistry	8.5	4	34
Coagulation	2.7	3	8.1
Serology	8.5	1	8.5
Genetic testing for mitochondrial mutations	5.4	1	5.4
PK	6	13	78
Extra volume for potential repeat draws or additional safety tests	-	-	50
Total Volume			196

Samples will be collected and processed as per the instructions given in the laboratory manual.

### 9.9.2 Urine Sample Collection and Processing

Urine samples will be collected for quantitation of unchanged ELX-02 at the following time or time intervals: pre-dose (first void in the morning of Day 1), 0-3, 3-6, 6-9, 9-12, 12-18, 18-24, 24-36, 36-48, and 48-72 hours post-dose. Urine samples will be collected as follows:

- At each void, all urine will be collected into a collection cup. The weight of each sample will be recorded and the volume of urine calculated assuming specific gravity of 1.
- Subjects will be asked to void their bladder within 10 minutes before the end of each collection interval, so that each new interval begins with an empty bladder.
- When a urine aliquot is needed at a specific timepoint for renal injury biomarkers and creatinine (pre-dose and at 12, 24, 36, and 48 hours post-dose), the aliquot will be withdrawn from the urine collection cup. If a subject is unable to void at the specified timepoint, it will be duly recorded and renal injury biomarkers and creatinine will be analyzed in the subsequent urine sample. Residual urine will be used for pooling with other voids of the same collection interval.
- All voids collected during a defined time interval will be pooled into one urine collection container. The sum of individual samples' weights will be recorded. Any urine voided by subjects at the intersection (within 10 minutes) of two intervals will be included in the earlier sample. Two aliquots will be taken in each pooled time interval container for PK analysis.
- Thereafter, all urine collected in the intervals 0-3, 3-6, 6-9, 9-12, 12-18, 18-24 will be pooled together to withdraw a sample for the calculation of creatinine clearance. The sum of all samples' weights will be recorded. Refer to section 9.10.8.

- At approximately 24 and 72 hours post-dose, a mid-stream safety sample will also be collected for urinalysis.
- Any urine voided by subjects but not collected will be documented.

Urine samples will be collected and processed as per the instructions given in the laboratory manual.

## **9.10 Subject Monitoring**

Subjects will be monitored throughout the study by the clinical sites staff for AEs. The PI or a Sub-Investigator will be on site/campus for drug administration and until 4 hours after administration of the study medication to the last subject. The PI or a Sub-Investigator will also be on call for the remainder of the study. If necessary, a physician, either at the clinical site or in a nearby hospital will administer treatment for any AE(s). A crash cart or emergency bag containing the necessary rescue material and appropriate medications will be available in the clinic to allow rapid intervention in case of emergency.

Safety parameters, including laboratory results and ECG, will be assessed by the PI or delegate, using the clinical site criteria for biomedical laboratory and ECG acceptance ranges as suggested guidelines in making the medical assessment.

Scheduled safety measurements will be repeated according to appropriate clinical site SOPs or upon request from a physician. Any abnormal repeated measurement will be evaluated by a physician and repeated if judged necessary. Further action may be taken upon physician's request.

Subjects will be advised to notify their health care professional(s) (e.g., physician, dentist, and/or pharmacist) that they are participating in a clinical research study on an experimental drug called ELX-02 being developed for the treatment of genetic diseases before taking any medicines or undergoing any medical procedure.

### **9.10.1 Vital Signs**

Blood pressure, respiratory rate, heart rate, and oral temperature will be measured after at least 5 minutes of sitting (except for safety reasons) at screening, at check-out on Day 4 and at study exit. Blood pressure, heart rate and oral temperature will also be measured prior to dosing and approximately 2, 4, 24, and 48 hours post-dose. When vital signs measurements coincide with a blood draw, they should preferably be performed before the blood collection whenever possible. A time window of 15-20 minutes for vital signs will be allowed if there are multiple procedures at the same time point.

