#### 4. Schedule of Events

**Table 1. Schedule of Events for Study Groups 1 to 4**

PROCEDURE	Screening	Groups 1 to 4					Study Exit (Follow-Up Visit on Day 8 ± 1) or Early Termination
		D-1	D1	D2	D3	D4	
Demographic Data	X						
Medical and Medication Histories	X						
Review and Monitoring of AEs and Concomitant Medications		X	X	X	X	X	X
Physical Examination	X	X				X	X
Body Measurements	X	X 					
Vital Signs (BP, HR, RR, OT)	X		X 	X 	X 	X 	X
ECG	X		X 			X 	X
Hematology	X	X 					X
Biochemistry	X	X 		X 			X
Serum Cystatin C Measurement	X						
Coagulation	X	X 					X
Urinalysis	X	X 		X		X	X
HIV and Hepatitis	X						
Genetic Testing for Mitochondrial Mutations	X						
Urine Drug Screen	X	X					
Urine Cotinine Test (for Group 4 only)	X	X					
Alcohol Test (Breath or Urine Test)	X	X					
Serum Pregnancy Test		X					
Urine Pregnancy Test	X						X
Injection Site Evaluation			X 	X 	X 	X 	X
In-Patient Stay		X	X	X	X		
Study Drug Administration			X				
PK Blood Samples			X	X	X	X	X
PK Urine Sample			X	X	X	X	
Urine Sample for Creatinine			X	X	X		X
Renal Injury Biomarkers			X	X	X		X

1 A complete physical examination will be performed at screening. A brief physical examination will be performed on Day -1, at check-out on Day 4 and at study exit.

2 Body weight only on Day -1.

3 BP, HR and OT: before dosing and approximately 2, 4, 24, and 48 hours post-dose. BP, HR, RR and OT: at check-out on Day 4.

4 ECG: pre-dose, approximately 2 hours post-dose and at check-out on Day 4.

5 Laboratory assessments (i.e., biochemistry, hematology, coagulation, and urinalysis) will be done in the morning of Day -1 following a fasting period of at least 8 hours.

6 Serum creatinine only: approximately 24 hours post-dose.

- 7 Cystatin C will be measured at screening and cystatin GFR will be estimated for additional data analysis, only if needed. These values will have no impact on subject's eligibility and categorization.
- 8 Injection site evaluation: before dosing and approximately 0.75, 2, 6, 12, 24, 36, 48, and 72 hours post-dose.

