### 9.1 Screening Procedures

Subject screening procedures will be performed within 35 days preceding administration of study medication. Subjects must provide written informed consent prior to initiation of any screening procedures. The consent to perform some general screening procedures may be obtained on a consent document other than the ICF specific to this study, and therefore, some screening test results could be obtained before signature of the ICF specific to this study. The study-specific ICF must be signed and dated by the subject before participation to study-specific procedures.

Screening procedures will include: demographic data, medical and medication histories, complete physical examination, body measurements, ECG (12-lead), vital signs (BP, HR, RR, OT), hematology, biochemistry, coagulation, HIV, hepatitis B and C tests, urinalysis, genetic testing for mitochondrial mutations, urine drug screen, alcohol test (breath or urine), urine pregnancy test, and urine cotinine test (for Group 4 only).

Serum cystatin C will be measured at screening and cystatin GFR will be estimated for additional data analysis, only if needed. These values will have no impact on subject's eligibility and categorization.

For eligibility purposes, abnormal laboratory or vital signs results may be repeated once (subjects of Groups 1 to 3 may need more repeats to confirm stability) if abnormal result is observed at the initial reading. Moreover, abnormalities found in the ECG may need to be confirmed by repeated measurements. In the event that the participation of a subject in the study is delayed and some screening procedures had been performed outside the prescribed screening window, outdated screening procedures can be repeated.

Subjects from Groups 1 to 3 (mild, moderate, and severe RI subjects) should be recruited prior to recruiting control group subjects in order to facilitate subjects' matching.

Subjects of Groups 1 to 3 who do not qualify based on a reversible condition or mild intercurrent illness may be re-evaluated after further testing/examination or re-screened after the condition is resolved.

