### 9.3 In-Patient Stay and Visit

Subjects will remain as in-patients from the morning of Day -1 until after the 72-hour post-dose blood draw. Subjects will come back for a follow-up visit on Day 8 (±1 day).

Participation of each subject in this study should last approximately 1 week (approximately 5 weeks including the screening visit).

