9.4 Vital Signs

Blood pressure, respiratory rate, heart rate and oral temperature will be measured in a sitting position after at least 5 minutes of sitting (except for safety reasons) at screening, at check-out on Day 4 and at study exit. Blood pressure, heart rate, and oral temperature will also be measured prior to dosing and approximately 2, 4, 24 and 48 hours post-dose.

Descriptive statistics (mean, median, SD, Min, Max, and sample size) will be presented by group and overall for screening, 2, 4, 24 and 48 hours post-dose and study exit for each vital sign measurement. Baseline will be defined as the last results (scheduled or unscheduled) obtained prior to the administration of ELX-02. Unscheduled results will not be included in the summary tables except for baseline calculation if applicable. Change from baseline descriptive statistics for post-dose measurements as well as for study exit will be presented. Results from repeat tests will not be included in the summary statistics unless the repeat was required (and documented as such) due to technical reasons or an invalid initial result.

A listing of all vital signs results will be provided by subject.

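### Respiratory rate is first taken about 72 h after dosing, against a screening baseline up to 35 days old, so its planned change from baseline cannot show an acute, exposure-related effect

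*Protocol*

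**What the plan says.** Protocol 9.10.1 sets two vital-sign schedules. Blood pressure, respiratory rate, heart rate and oral temperature are taken "at screening, at check-out on Day 4 and at study exit". A shorter set, without respiratory rate, covers the dosing period: "Blood pressure, heart rate and oral temperature will also be measured prior to dosing and approximately 2, 4, 24, and 48 hours post-dose". The synopsis and Table 1 footnote 3 repeat this and bring respiratory rate back only at discharge: "BP, HR, RR and OT: at check-out on Day 4". The Table 1 row heading lists all four signs and is marked on Days 1 to 3, but footnote 3 narrows those marks. No vital signs are scheduled on Day -1.

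Two other sections fix the timing. On screening, Protocol 9.1 says: "Subject screening procedures will be performed within 35 days preceding administration of study medication". On discharge, Protocol 9.3 keeps subjects in the clinic "until after the 72-hour post-dose blood draw".

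SAP 9.4 repeats the measurement schedule and then sets the analysis:

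- Baseline: "Baseline will be defined as the last results (scheduled or unscheduled) obtained prior to the administration of ELX-02".
- Summary times: "screening, 2, 4, 24 and 48 hours post-dose and study exit for each vital sign measurement".
- Change scores: "Change from baseline descriptive statistics for post-dose measurements as well as for study exit will be presented".

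Unscheduled results enter the summaries only where they serve as baseline. All vital-sign results are also listed by subject.

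**The concern.** Safety and tolerability form the secondary objective, and Protocol 12.3.2 names vital signs among the parameters that address it. For blood pressure, heart rate and temperature, the plan compares values at 2 h and 4 h with a value taken before dosing on the same day. For respiratory rate it compares a value at about 72 h with one taken up to five weeks earlier, yet SAP 9.4 treats all four signs alike.

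A reader of the vital-sign tables could take an unchanged respiratory rate as evidence about the period of exposure when no scheduled value comes from the hours near the peak. This matters most in the severe group, where exposure is expected to be highest. The protocol also treats neuromuscular function as relevant to this drug: it excludes subjects with recent neuromuscular blockade (8.2.2 and 8.3.2) and prohibits neuromuscular blocking agents in its concomitant-medication rules (9.8.3). It does not say that it expects a respiratory effect at this dose.

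**Working it through.** The plan states no figure for this point, so there is none to reproduce. The check sets the schedules side by side and then relates the measurement times to drug exposure.

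**Schedule**

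| Time | BP, HR, temperature | Respiratory rate | Named in the SAP 9.4 summary list |
|---|---|---|---|
| Screening (up to 35 days before dosing) | yes | yes | yes |
| Pre-dose, Day 1 | yes | no | no |
| 2, 4, 24, 48 h | yes | no | yes |
| Day 4 check-out (about 72 h) | yes | yes | no |
| Study exit (Day 8 ±1) | yes | yes | yes |

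Four of the six times that SAP 9.4 lists (2, 4, 24 and 48 h) have no scheduled respiratory rate. Of the five post-dose sets up to Day 4, respiratory rate is in one, and that one is not listed. On the wording of that sentence, the first post-dose respiratory rate to be summarised is study exit. SAP 9.5 names both pre-dose and Day 4 for ECG.

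**Age of the comparison.** From baseline to Day 4: up to 35 + 3 = 38 days. From baseline to study exit: up to 35 + 7 = 42 days, or 43 with the one-day window.

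**Exposure in subjects with normal renal function.** Inputs from Protocol 5.2.2.2 for 1 mg/kg SC: median Tmax 1.0 h, half-life 2.14 h. Fraction of peak left at time T = 2^(−(T − 1)/half-life).

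- 2 h: 2^(−1/2.14) = 72%
- 4 h: 2^(−3/2.14) = 38%
- 72 h: 2^(−71/2.14) = 1.0e-10

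The half-life is printed with an SD equal to its mean, so the check was repeated at 4 h, the upper end of the 2 to 4 h range that Protocol 5.1.2 gives for doses up to 5 mg/kg. This leaves 84% at 2 h, 59% at 4 h and 2^(−71/4) = 4.5e-6 at 72 h.

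**Exposure in severe impairment (assumed scaling).** The documents give no half-life for this group. Assume that clearance falls in proportion to eGFR for the renally eliminated fraction fe, that volume is unchanged, that normal eGFR is 105, and that the peak stays at 1 h. Then half-life = 2.14/(1 − fe × (1 − eGFR/105)). Protocol 5.1.2 reports urinary recovery of 81.1 to 99.2% after SC doses, so fe is taken as 0.81 to 0.99.

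| eGFR | Half-life (h) | Left at 2 h | Left at 4 h | Left at 72 h |
|---|---|---|---|---|
| 22 | 5.9–9.8 | 89–93% | 71–81% | 0.03–0.7% |
| 15 | 7.0–14.1 | 91–95% | 74–86% | 0.09–3.1% |
| 10 | 8.0–20.5 | 92–97% | 77–90% | 0.2–9% |

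Worked case, eGFR 15 and fe 0.99: 2.14/(1 − 0.99 × 0.857) = 14.1 h, and 2^(−71/14.1) = 3%.

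**The case against.** The respiratory-rate schedule is the same in Protocol 9.10.1, the synopsis, Table 1 footnote 3 and SAP 9.4, so it looks deliberate. No visible text predicts an acute respiratory effect at 1 mg/kg, and part of the background is redacted. Early safety is watched in other ways: subjects are in-patients to 72 h, adverse events are monitored throughout, a physician is on site or campus until 4 h after dosing, and measurements can be repeated on request. Overt respiratory change would surface as an adverse event. With about six subjects per group and no placebo arm, a mean at 2 h would itself be weak evidence. All of this stands, and it keeps the point small. It does not supply data for the 2–48 h summaries.

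Four stronger readings are tempting, and the documents do not support them:

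- **Respiratory rate can show no drug effect at all.** A delayed or persistent change could still appear on Day 4 or at exit, plasma level is not the same as effect, and some drug may remain at 72 h at very low eGFR. Such a change would be hard to attribute, because there is neither a same-day baseline nor a placebo arm.
- **The report will declare respiratory rate unaffected.** Nothing says so. Safety reporting is descriptive, and labelled times would let a reader see the gap.
- **The Day 4 omission is specific to respiratory rate, or the value is lost.** It affects all four vital signs. The change-from-baseline sentence in SAP 9.4 can be read to include Day 4, all results are listed, and the table shells are in a separate document.
- **The baseline is always 35 days old, or its definition is wrong.** Thirty-five days is the maximum, and an unscheduled pre-dose value would count. The definition is sound; respiratory rate lacks a scheduled Day 1 value for it to select.

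**Conclusion.** The concern holds for acute, exposure-related effects. As scheduled, the change from baseline in respiratory rate compares a value at about 72 h or later with one up to 35 days before dosing. By 72 h about 1e-10 of peak remains at the stated half-life. In severe impairment the figure is roughly 0.1–3% for half-lives of about 7–14 h, and higher at very low eGFR. The schedule facts and the control figures rest on the documents, subject to the doubtful SD of the half-life. The severe-group figures rest on the assumed scaling and show order of magnitude only.

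SAP 9.4 is also out of step with the schedule: it plans summaries of respiratory rate at four times with no scheduled data, and it leaves pre-dose and Day 4 off its list for every vital sign. This is a cheap improvement to one descriptive secondary safety variable. The PK analyses are unaffected.

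**What to change.** In Protocol 9.10.1, the synopsis and Table 1 footnote 3, record respiratory rate with the blood pressure, heart rate and temperature sets already scheduled pre-dose and at 2, 4, 24 and 48 h. The existing SAP baseline rule then selects the Day 1 value without rewording. In SAP 9.4, add pre-dose and Day 4 check-out to the summary times for all four vital signs, as SAP 9.5 does for ECG.

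If dosing is already past, make the SAP 9.4 addition and state there and in the report that respiratory rate has no same-day baseline and no early post-dose data, so its change from baseline does not address acute effects.

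Cost: about one minute per existing set (five sets per subject), a few CRF fields, and short wording changes. No new visit, sample or staff is needed. The late option costs wording only.

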### **9.10.2 ECG**

12-lead ECG will be performed at screening, prior to dosing, approximately 2 hours post-dose, at check-out on Day 4 and at study exit. ECG will be performed after a resting time of at least 5 minutes in supine position. When ECG coincides with a blood draw, it should preferably be performed before the blood collection whenever possible. A time window of 15-20 minutes for ECG will be allowed if there are multiple procedures at the same time point.

### **9.10.3 Physical Examination and Body Measurements**

A complete physical examination will be performed at screening. A complete physical examination includes assessments of at least the following: head, eyes, ears, nose, throat (HEENT), neck, chest, lungs, abdomen, musculoskeletal, dermatological, cardiovascular/peripheral vascular, and general neurological examination.

A brief physical examination will be done on Day -1, at check-out on Day 4 and at study exit. A brief physical examination includes assessments of the following: HEENT, chest, lungs, abdomen, dermatological, cardiovascular/peripheral vascular, and areas of note elicited from the subject.

Body weight and height will be measured at screening and the BMI calculated. Body weight measurement will be done again on Day -1 and this value will be used to calculate the exact individual dose of ELX-02 required on a mg/kg basis.

### **9.10.4 Injection Site Evaluation**

Local reactions at the injection site will be evaluated by a trained observer and recorded: prior to study drug injection, approximately 0.75, 2, 6, 12, 24, 36, 48, and 72 hours hours post-dose, and at study exit. The extent of local reaction at the injection site will be graded according to the Division of AIDS (DAIDS) criteria presented in [APPENDIX 1](#).

### **9.10.5 Drug, Alcohol and Cotinine Screen**

A urine drug screen (amphetamines, methamphetamines, barbiturates, benzodiazepines, tetrahydrocannabinol, cocaine, opiates, PCP, MDMA, methadone) and an alcohol test (breath or urine) will be performed at screening and on Day -1. For Group 4 only, a urine cotinine test will also be performed at screening and on Day -1.

### **9.10.6 Pregnancy Test**

A urine pregnancy test will be performed at screening and at study exit, and a serum pregnancy test will be performed on Day -1.

### **9.10.7 Laboratory Assessments**

Procedures of processing and storing clinical laboratory samples will be detailed in the laboratory manual.

